### 9.5.2 Safety variables

Safety evaluations to be analyzed are listed as below:

- Change from baseline in a cortical composite SUVr (standardized uptake value ratio) at 3 years

■ [REDACTED]

[REDACTED]

### **Analysis on change from baseline in SUVR at 3 years**

In order to make the most use of data collected from all available PET scan assessments, including the planned ‘end-of-treatment’ and ‘end-of-study’ assessments, the analysis of change from baseline (randomization) in a cortical composite SUVR at 3 years (Week 156) will be based on a model-based multiple imputation approach under MAR (missing at random) assumption.

The imputation model will include age stratification factor, MMSE stratification factor, region, baseline cerebrovascular disease burden as measured by MRI, APOE4 status (carrier vs non-carrier), and time (when the SUVR is assessed in days) as fixed effects with random intercept and slope (time) and a common unstructured covariance. This will be done separately within each treatment by baseline amyloid status (positive/negative). This imputation process will first create multiple imputations of missing SUVR at 3 years under a MAR assumption, resulting in multiple complete data sets after combining the imputed missing SUVR at 3 years values with the available SUVR at 3 years (so every patient with baseline SUVR in these multiple complete data sets have an SUVR value at 3 years).

An ANCOVA model using change from baseline to 3 years in SUVR as response variable, with treatment, age stratification factor, MMSE stratification factor, region, baseline cerebrovascular disease burden as measured by MRI, APOE4 status, baseline amyloid status as factors and baseline SUVR value as covariate will be run on each of these multiple completed data sets. Overall results and inference, including adjusted mean change at 3 years within each treatment, the difference in mean change at 3 years between two treatments, its 95% confidence interval, are obtained by applying Rubin’s rules on the estimates obtained from the imputed/completed data sets.

[figure not shown]
As sensitivity analysis, the change in a cortical composite SUVR from baseline to 3 years will also be analyzed based on a repeated measures ANCOVA model in which treatment, age stratification factor, MMSE stratification factor, region, baseline cerebrovascular disease burden as measured by MRI, APOE4 status (carrier vs. non-carrier), baseline amyloid status (positive/negative), visit (18 months, 3 years), and treatment-by-visit interaction will be included as fixed-effect factors and baseline value and baseline-by treatment as covariates, with a common unstructured covariance matrix among visits between treatment group. The adjusted mean changes at 3 years (Week 156) within each treatment, the difference in mean changes at 3 years (Week 156) between two treatments, its 95% confidence interval obtained from the above model will be presented. The analysis is based on likelihood method with an assumption of missing at random for missing data. A three month window will be applied to re-map any unscheduled visit assessments to a missing scheduled visit assessment.

In addition, to assess the sensitivity of the MAR assumption used in multiple imputation, analyses based on multiple imputations, such as those using a pattern mixture model approach,

may be performed, which assumes that missing values after death, HF hospitalizations, stroke were missing not at random (MNAR).

A shift table to summarize the proportion of patients' amyloid status change over time from baseline by treatment will be provided as well.

All analyses will be performed in patients in the Safety set who participate in the PET image substudy, including 'on-treatment' data only. On-treatment data refer to the SUVR values obtained while patients are on-study-medication (regardless of treatment interruption) or within six months after final study drug intake date.

[figure not shown]

**9.5.3 Resource utilization**

Not applicable

**9.5.4 Pharmacokinetics**

Not Applicable

### 9.5.6 Biomarkers

[figure not shown]
For plasma A $\beta$ 1-40, the log-transformed ratio to baseline will be calculated for each subject at every post-dose time point, i.e.  $\log(\text{post-dose value}/\text{baseline})$ . The change from baseline to a pre-defined time-point (Weeks 13, 52, 104 and 156) in logarithmic scale will be analyzed using the same repeated measures ANCOVA model as for the primary endpoint but with baseline GCCS replaced with baseline biomarker values in logarithmic scale. The adjusted mean changes at each visit within each treatment, the difference in mean changes between two treatments, its 95% confidence interval obtained from the above model will be provided. These estimates and confidence intervals will be back-transformed for presentation.

[figure not shown]
Summaries of absolute values and change from baseline in A $\beta$ 1-40 by treatment group and visit will be presented using statistics: n, mean, SD, median, minimum, maximum, Q1, Q3, geometric mean and Coefficient of Variation. Figures will be produced to visually show the mean A $\beta$ 1-40 levels by visit over study period for each treatment group.

All of the above analyses will be performed for patients for whom the biomarker data is obtained in the Full analysis set including all data.

### 9.5.7 PK/PD

Not applicable

## 9.7 Interim analyses

No formal interim efficacy analyses are planned. Refer to [Section 8.4](#) for planned regular interim safety data review by an independent Data Monitoring Committee.

## 9.8 Sample size calculation

### 9.8.1 Sample size calculation for the primary endpoint

It is currently estimated that approximately 180 patients per group

- would provide at least 80% probability that the 2-sided 95% confidence interval (CI) excludes a standardized effect size (Cohen's d) of 0.3 (or greater) in change in composite z-score of the battery test over 3 years, given that there is no expected difference between two treatments.
- Would provide at least 80% probability that the 2-sided CI excludes 0 (corresponding to  $p < 0.05$ ), if the true effect size is 0.3 or greater (in either direction).

An effect size of 0.3 in Cohen's d corresponds to a margin of  $0.3 \times \text{SD}$  (SD=standard deviation) on the original scale for the difference between treatments in mean global score change from baseline, and is generally considered as small ([Cohen 1988](#)). In a systematic review of studies for health-related quality of life instruments that have reported the minimally important difference (MID), it was found that for the majority of studies the MID estimates were consistently close to  $0.5 \times \text{SD}$  ([Norman et al 2003](#)). In addition, socially accepted benchmarks for conditions that induce cognitive impairment such as low level alcohol intoxication within legal driving limit in most countries (0.05%) are generally associated with declines of 0.3 or higher for psychomotor speed, attention and working memory. Therefore, the sample size of the study was determined to be able to detect (or exclude) effect sizes in the magnitude of 0.3 in Cohen's d with high probability, as it appears to be an appropriate choice to guide the interpretation of the cognitive function results.

In addition, defining the magnitude of the MID using a measure of effect size, rather than a raw difference score has additional advantages:

- Expressing the magnitude of an important difference in scale free units (Cohen's d) allows models of clinically meaningful difference to be based on integration of outcomes from a broad set of studies whose characteristics are relevant to the current study (i.e. magnitude of change in cognition related to amyloid, magnitude of change occurring after heart failure, and magnitude of change related to cardiovascular disease).
- Estimates of clinically meaningful difference can be referenced to the magnitude of cognitive decline detected from studies where compounds with accepted central nervous system adverse effects, at known doses are administered to older adults (e.g. scopolamine, alprazolam).

Sample size calculation was performed using N-Query 7.0.

### 9.8.2 Sample size calculation for the PET imaging substudy

Approximately 300 patients (in 1:1 allocation ratio to LCZ696 and valsartan) will provide at least 80% probability that the 2-sided 95% CI excludes a between-treatment absolute

difference of 0.01 (corresponding to an incremental 33% increase in LCZ696 vs. valsartan) in change from baseline in SUVR over 3 years if there is no expected difference between two treatments. This calculation is based on the assumptions that the mean change over 3 years from baseline in SUVR is 0.03 in the control group, the common standard deviation is 0.03 (estimated from ADNI data, [Chen et al 2015](#)). It is noted that the ADNI data presented in Chen's paper are by patients' cognitive status (normal, MCI, dementia) and for changes over two years. The assumptions used here are guestimates from the 2 year data in normal cognitive and MCI subjects.

An absolute difference in SUV ratio of 0.01 was considered small as it represents a value that is lower than the rate of SUVR change that distinguishes between amyloid positive and negative patients (0.026 vs. 0.011).

Sample size calculation was performed using N-Query 7.0.

### **9.8.3 Blinded sample size re-estimation**

Approximately 520 patients will be randomized in order to provide overage to account for the information loss caused by an estimated 30% "drop-out" (including death, lost-to-follow-up, permanent discontinuation of study medication and start of treatments for AD or cognitive impairment) during 3 year period. In the PET imaging substudy approximately 430 patients will be randomized.

A loss of 30% of information is a crude estimate therefore it is planned to monitor the 'drop-out' pattern as the trial is ongoing in order to provide a better prediction of the information loss for a given number of patients. The final number of patients randomized may be reduced if there is sufficient evidence that the information loss will be less than 30% and that the precision of the estimates of treatment effect (as described in the sample size section above), will be maintained.

## **10 Ethical considerations**

### **10.1 Regulatory and ethical compliance**

This clinical study was designed and shall be implemented, executed and reported in accordance with the ICH Harmonized Tripartite Guidelines for Good Clinical Practice, with applicable local regulations (including European Directive 2001/20/EC, US CFR 21, and Japanese Ministry of Health, Labor, and Welfare), and with the ethical principles laid down in the Declaration of Helsinki.

### **10.2 Informed consent procedures**

Eligible patients/subjects may only be included in the study after providing written (witnessed, where required by law or regulation), IRB/IEC-approved informed consent. He/she must indicate assent by personally signing and dating the written informed consent document or a separate assent form. Informed consent must be obtained before conducting any study-specific procedures (e.g. all of the procedures described in the protocol). The process of obtaining informed consent must be documented in the patient source documents.

Novartis will provide to investigators in a separate document a proposed informed consent form that complies with the ICH GCP guideline and regulatory requirements and is considered appropriate for this study. Any changes to the proposed consent form suggested by the investigator must be agreed to by Novartis before submission to the IRB/IEC, and a copy of the approved version must be provided to the Novartis monitor after IRB/IEC approval.

[REDACTED]

### **10.3 Responsibilities of the investigator and IRB/IEC**

Before initiating a trial, the investigator/institution must obtain approval/favorable opinion from the Institutional Review Board/Independent Ethics Committee (IRB/IEC) for the trial protocol, written informed consent form, consent form updates, subject recruitment procedures (e.g., advertisements) and any other written information to be provided to patients/subjects. Prior to study start, the investigator is required to sign a protocol signature page confirming his/her agreement to conduct the study in accordance with these documents and all of the instructions and procedures found in this protocol and to give access to all relevant data and records to Novartis monitors, auditors, Novartis Quality Assurance representatives, designated agents of Novartis, IRBs/IECs, and regulatory authorities as required. If an inspection of the clinical site is requested by a regulatory authority, the investigator must inform Novartis immediately that this request has been made.

### **10.4 Publication of study protocol and results**

The key design elements of this protocol will be posted in a publicly accessible database such as clinicaltrials.gov. In addition, upon study completion and finalization of the study report the results of this trial will be either submitted for publication and/or posted in a publicly accessible database of clinical trial results.

### **10.5 Quality control and quality assurance**

Novartis maintains a robust Quality Management (QM) system that includes all activities involved in quality assurance and quality control, including the assignment of roles and responsibilities, the reporting of results, and the documentation of actions and escalation of issues identified during the review of quality metrics, incidents, audits and inspections.

Audits of investigator sites, vendors, and Novartis systems are performed by Novartis Pharma Auditing and Compliance Quality Assurance (CQA), a group independent from those involved in conducting, monitoring or performing quality control of the clinical trial. The clinical audit process uses a knowledge/risk based approach.

Audits are conducted to assess GCP compliance with global and local regulatory requirements, protocols and internal SOPs, and are performed according to written Novartis processes.

[REDACTED]

## 11 Protocol adherence

This protocol defines the study objectives, the study procedures and the data to be collected on study participants. Additional assessments required to ensure safety of patients/subjects should be administered as deemed necessary on a case by case basis. Under no circumstances is an investigator allowed to collect additional data or conduct any additional procedures for any research related purpose involving any investigational drugs under the protocol.

Investigators ascertain they will apply due diligence to avoid protocol deviations. If an investigator feels a protocol deviation would improve the conduct of the study this must be considered a protocol amendment, and unless such an amendment is agreed upon by Novartis and approved by the IRB/IEC and health authorities, where required, it cannot be implemented.

### 11.1 Protocol amendments

Any change or addition to the protocol can only be made in a written protocol amendment that must be approved by Novartis, health authorities where required, and the IRB/IEC prior to implementation. Only amendments that are intended to eliminate an apparent immediate hazard to patients/subjects may be implemented immediately provided the health authorities are subsequently notified by protocol amendment and the reviewing IRB/IEC is notified. Notwithstanding the need for approval of formal protocol amendments, the investigator is expected to take any immediate action required for the safety of any patient included in this study, even if this action represents a deviation from the protocol. In such cases, the reporting requirements identified in [Section 7](#) Safety Monitoring must be followed.

## 14 Appendix 2: Liver event definition and follow-up requirements

**Table 14-1 Liver event definitions**

	Definition/ threshold
AE of special interest Laboratory values	
 
ALT or AST > 3 x ULN
 
ALP > 2 x ULN
 
TBL > 1.5 x ULN
 

Medically significant event (SAE) Laboratory values	
 
ALT or AST > 5 x ULN (with or without TBL > 2 x ULN [mainly conjugated fraction])
 
ALP > 5 x ULN (with or without TBL > 2 x ULN [mainly conjugated fraction])
 
TBL > 3 x ULN
 
Potential Hy's Law cases (defined as ALT/AST > 3 x ULN and TBL > 2 x ULN [mainly conjugated fraction] without notable increase in ALP to > 2 x ULN)
 

AEs	
 
Any clinical event of jaundice (or equivalent term)
 
ALT or AST > 3 x ULN accompanied by (general) malaise, fatigue, abdominal pain, nausea, or vomiting, or rash with eosinophilia
 
Any adverse event potentially indicative of a liver toxicity*
 

\*These events cover the following: hepatic failure, fibrosis and cirrhosis, and other liver damage-related conditions; the non-infectious hepatitis; the benign, malignant and unspecified liver neoplasms  
TBL: total bilirubin; ULN: upper limit of normal

**Table 14-2 Follow up requirements for liver events**

Criteria	Event type	Actions required	Follow-up monitoring
Potential Hy's Law case a	Medically significant	Discontinue the study drug immediately Hospitalize, if clinically appropriate Report to Novartis as an SAE Establish causality	ALT, AST, TBL, Alb, PT, ALP and $\gamma$ GT until resolution c (frequency at investigator discretion)
ALT or AST			
> 8 x ULN	Medically significant	Repeat LFT within 48 hours If elevation persists, discontinue the study drug immediately Hospitalize if clinically appropriate Report to Novartis as an SAE Establish causality	ALT, AST, TBL, Alb, PT, ALP and $\gamma$ GT until resolution c (frequency at investigator discretion)
> 5 to $\leq$ 8 x ULN	Medically significant	Repeat LFT within 48 hours If elevation persists for more than 2 weeks, discontinue the study drug Report to Novartis as an SAE Establish causality	ALT, AST, TBL, Alb, PT, ALP and $\gamma$ GT until resolution c (frequency at investigator discretion)
> 3 x ULN accompanied by symptoms b	Medically significant	Discontinue the study drug immediately Hospitalize if clinically appropriate Report to Novartis as an SAE	ALT, AST, TBL, Alb, PT, ALP and $\gamma$ GT until resolution c (frequency at investigator discretion)

Criteria	Event type	Actions required	Follow-up monitoring
		Establish causality	discretion)
> 3 to ≤ 5 x ULN (patient is asymptomatic)	Adverse event of special interest (AESI)	Central laboratory to report to Investigator & Novartis Repeat LFT once or twice in the week If elevation persists, establish causality	Investigator discretion Monitor LFT within 1 to 4 weeks or at next visit
≤ 3 x ULN (patient is asymptomatic)	N/A	Repeat LFT at next visit	
ALP (isolated)			
> 5 x ULN	Medically significant	Repeat LFT within 48 hours If elevation persists, report to Novartis as an SAE Establish causality	Investigator discretion Monitor LFT within 1 to 4 weeks or at next visit
> 2 to ≤ 5 x ULN (patient is asymptomatic)	AESI	Central laboratory to report to Investigator & Novartis Repeat LFT once or twice in the week. If elevation persists, establish causality	Investigator discretion Monitor LFT within 1 to 4 weeks or at next visit
≤ 2 x ULN (patient is asymptomatic)	N/A	Repeat LFT at next visit	
TBL (isolated)			
> 3 x ULN	Medically significant	Repeat LFT within 48 hours If elevation persists, discontinue the study drug immediately Hospitalize if clinically appropriate Report to Novartis as an SAE Establish causality	ALT, AST, TBL, Alb, PT, ALP and γGT until resolution c (frequency at investigator discretion) Test for hemolysis (e.g., reticulocytes, haptoglobin, unconjugated [indirect] bilirubin)
> 1.5 to ≤ 3 x ULN (patient is asymptomatic)	AESI	Central laboratory to report to Novartis Repeat LFT once or twice in the week. If elevation persists, establish causality	Investigator discretion Monitor LFT within 1 to 4 weeks or at next visit
≤ 1.5 x ULN (patient is asymptomatic)	N/A	Repeat LFT at next visit	
Preferred terms			
Jaundice	Medically significant	Discontinue the study drug immediately Hospitalize the patient Report to Novartis as an SAE Establish causality	ALT, AST, TBL, Alb, PT, ALP and γGT until resolution c (frequency at investigator discretion)
"Drug-related hepatic disorders - severe events only" SMQ AE	Medically significant	Discontinue the study drug Hospitalization if clinically appropriate Report to Novartis as an SAE Establish causality	Investigator discretion

a Elevated ALT/AST > 3 x ULN and TBL > 2 x ULN but with no notable increase in ALP to > 2 x ULN
 
b General malaise, fatigue, abdominal pain, nausea, or vomiting, rash with eosinophilia
 
c Resolution is defined as an outcome of one of the following: return to baseline values, stable values at three subsequent monitoring visits at least 2 weeks apart, remain at elevated level after a maximum of 6 months, liver transplantation, and death.
			

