**Table 3-2 Safety monitoring criteria that must be met at Visit 1 (screening), Visit 103 and Visit 199/201**

Parameter	Visit 1 (Screening)	Visits 103 (treatment run-in) and Visit 199/201 (end of treatment run-in/randomization)
Potassium level	K ≤5.2 mmol/L (mEq/L)	K ≤5.4 mmol/L (mEq/L)
Kidney function	eGFR ≥30 mL/min/1.73m 	eGFR ≥25 mL/min/1.73m  eGFR reduction <35% compared to Visit 1
Blood pressure	SBP ≥110 mmHg	No symptomatic hypotension as determined by the investigator and SBP ≥100 mmHg.
AEs or conditions	No conditions that preclude continuation according to the investigator's judgment	No postural symptoms or any AEs that preclude continuation according to the investigator's judgment

AE – adverse event

To assess the patient's eligibility to continue in the study, either local or central laboratory should be used for the assessment of potassium and estimated glomerular filtration rate (eGFR) at Visits 103 and 199/201 (end of treatment run-in visit/randomization). If central laboratory is used, since it may take up to 72 hours to obtain the results, it is recommended that the site take this into consideration when scheduling subsequent study visits, while keeping the patient on the study medication. If a local laboratory is selected, the same samples should also be sent to the central laboratory, while the evaluation should be solely based on the local laboratory results. Patients should NOT enter Visits 103 or 199/201 without evaluating the safety monitoring criteria (Table 3-2).

Down-titration of study drug is not allowed during the treatment run-in period. Patients who are not able to tolerate study drug at the doses prescribed during the treatment run-in epoch will be discontinued.

Investigators may consider adjusting (dose reduced or discontinued) background medications (e.g., diuretic(s), antihypertensive agents, cardiovascular medications such as beta blockers, MRAs, nitrates, etc.) if the study drug is not tolerated (e.g., occurrence of AEs such as hyperkalemia, hypotension, and renal dysfunction) to ensure patients meet the safety criteria in [Table 3-2](#) during the treatment run-in epoch. Patients may be seen at any time for unscheduled visits during the treatment run-in epoch for re-evaluation of safety criteria parameters.

Patients who experience angioedema at any time during the treatment run-in epoch must be discontinued from the study.

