### **7.2.2 SAE reporting**

To ensure patient safety, every SAE, regardless of causality, occurring after the patient has provided informed consent and until 30 days following the last administration of study treatment must be reported to Novartis within 24 hours of learning of its occurrence. Any SAEs experienced after the 30 days period following the last administration of study treatment should only be reported to Novartis if the investigator suspects a causal relationship to study treatment.

All follow-up information for the SAE including information on complications, progression of the initial SAE and recurrent episodes must be reported as follow-up to the original episode within 24 hours of the investigator receiving the follow-up information. An SAE occurring at a different time interval or otherwise considered completely unrelated to a previously reported one must be reported separately as a new event.

Information about all SAEs is collected and recorded on the Serious Adverse Event Report Form; all applicable sections of the form must be completed in order to provide a clinically thorough report. The investigator must assess the relationship of each SAE to each specific component of study treatment, (if study treatment consists of several components) complete the SAE Report Form in English, and submit the completed form within 24 hours to Novartis. Detailed instructions regarding the submission process and requirements for signature are to be found in the investigator folder provided to each site.

Follow-up information is submitted as instructed in the investigator folder. Each re-occurrence, complication, or progression of the original event must be reported as a follow-up to that event regardless of when it occurs. The follow-up information should describe whether the event has resolved or continues, if and how it was treated, whether the blind was broken or not, and whether the patient continued or withdrew from study participation.

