### **7.3 Liver safety monitoring**

To ensure patient safety and enhance reliability in determining the hepatotoxic potential of an investigational drug, a standardized process for identification, monitoring and evaluation of liver events has to be followed. Liver events are divided into two categories:

- Liver events of special interest which consist of liver function test (LFT) elevations

- Medically significant liver events which are considered as SAEs and which consist of marked elevations of LFTs and / or pre-specified AEs.

Please refer to [Table 14-1](#) in [Appendix 2](#) for complete definitions of liver events.

Any liver event which meets the criteria for “medically significant” event as outlined in [Table 14-1](#) of [Appendix 2](#) should follow the standard procedures for SAE reporting as described in [Section 7.2](#).

Every liver event as defined in [Table 14-1](#) of [Appendix 2](#) should be followed up by the investigator or designated personnel at the trial site as summarized below. Detailed information is outlined in [Table 14-2](#) in [Appendix 2](#).

- Repeating the LFT to confirm elevation as appropriate
- Discontinuation of the investigational drug if appropriate
- Hospitalization of the patient if appropriate
- A causality assessment of the liver event via exclusion of alternative causes (e.g., disease, co-medications)
- An investigation of the liver event which needs to be followed until resolution.

These investigations can include serology tests, imaging and pathology assessments, hepatologist’s consultancy, based on investigator’s discretion. All follow-up information, and the procedures performed should be recorded on appropriate CRF pages, including the liver event overview CRF pages.

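### For an isolated ALP above 5 x ULN, Table 14-2 makes the SAE report wait on a repeat test, while Table 14-1 with Sections 7.3 and 7.2.2 requires it within 24 hours on the first value

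*Protocol*

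**What the plan says.** Four places in the protocol govern this laboratory value.

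- **Table 14-1 (Appendix 2, definitions).** Under the heading "Medically significant event (SAE) Laboratory values" it lists ALP above 5 x ULN, whether or not bilirubin is also raised. That wording includes an isolated ALP rise. No repeat or persistence condition is attached.
- **Section 7.3 (liver safety monitoring).** One of its two categories is "Medically significant liver events which are considered as SAEs and which consist of marked elevations of LFTs", with or without pre-specified AEs. An event meeting the Table 14-1 criteria for this category "should follow the standard procedures for SAE reporting as described in" Section 7.2. Separately, among the follow-up steps for a liver event, it lists "Repeating the LFT to confirm elevation as appropriate".
- **Section 7.2.2 (SAE reporting).** Every SAE, whatever its cause, "must be reported to Novartis within 24 hours of learning of its occurrence". Later information on the same event "must be reported as follow-up to the original episode within 24 hours of the investigator receiving the follow-up information".
- **Table 14-2 (Appendix 2, actions), isolated ALP above 5 x ULN.** The event type is again medically significant. The actions are a repeat liver test within 48 hours, then "If elevation persists, report to Novartis as an SAE", then a causality assessment.

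**The concern.** One laboratory value carries two reporting rules. Table 14-1 and Sections 7.3 and 7.2.2 together create a duty that starts at the first value and runs out after 24 hours. The Table 14-2 row creates a duty that exists only if a second test, taken up to 48 hours later, is still raised.

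Table 14-2 is the sheet a site would have in hand when an abnormal result arrives. A coordinator who follows it literally waits for the repeat. The report may then miss the 24-hour limit, or never be made if the value falls. What is at stake is the timeliness and completeness of mandatory SAE reporting. No bias between arms is suggested, and the primary GCCS and SUVr analyses do not use this information.

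**Working it through.** **Step 1. The rules side by side for an isolated ALP above 5 x ULN**

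| Source | Is the first value an SAE? | Condition for reporting | Time limit |
|---|---|---|---|
| Table 14-1 with Section 7.3 | Yes | None | Sent to Section 7.2 |
| Section 7.2.2 | Applies to every SAE | None | 24 h from learning of it |
| Table 14-2, isolated-ALP row | Labelled medically significant | Elevation must persist on repeat | Repeat within 48 h |

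**Step 2. Is the condition really on the report?** In the ALP row the condition and the instruction to report form one sentence, joined by a comma, so this is not an effect of text extraction. The other medically significant rows differ:

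- For ALT or AST above 8 x ULN, ALT or AST above 5 and up to 8 x ULN, and isolated bilirubin above 3 x ULN, persistence governs stopping the study drug. The SAE report is a separate action with no condition.
- The rows for potential Hy's Law cases, symptomatic ALT or AST elevation, jaundice and severe drug-related hepatic disorders have no persistence condition at all.

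The ALP row is therefore the only medically significant row in which the SAE report depends on a repeat test.

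**Step 3. Value that does not persist.** Table 14-1 with Section 7.3 gives 1 SAE. The Table 14-2 row gives 0.

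**Step 4. Value that persists.** Inputs:

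- Reporting deadline D = 24 h (Section 7.2.2).
- Time of repeat R = 0 to 48 h after the site learns of the first value (Table 14-2).
- Result turnaround T. The documents give none for liver tests. Section 3.1, after Table 3-2, says of central-laboratory potassium and eGFR: "since it may take up to 72 hours to obtain the results". Using 72 h for liver tests is an assumption, so T is taken from 0 to 72 h.

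If the report is filed as soon as the repeat result is known, and the clock is not restarted at confirmation:

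hours late = max(0, R + T − D)

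- T = 0, R up to 24 h: 0 h late.
- T = 0, R = 48 h: 48 + 0 − 24 = 24 h late.
- T = 72 h, R = 48 h: 48 + 72 − 24 = 96 h late.

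The range is thus 0 to 24 h with an immediate result, and up to 96 h if the 72 h turnaround applied to liver tests.

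**Step 5. Can a site satisfy both rules?** Yes, by reporting within 24 hours on the first value and repeating afterwards. But then the condition in the row has no effect.

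**The case against.** The best counter-argument is that confirmation first is a deliberate sponsor rule. Table 14-1 defines and Table 14-2 directs action, Section 7.3 points to Table 14-2 for detail, and repeating the test comes first in its list of follow-up steps. The ALP row is also lighter than the other medically significant laboratory rows: it has no drug discontinuation and no hospitalization, and monitoring is left to the investigator. On that reading the event exists only once confirmed, the 24-hour clock starts then, and nothing is late. In addition, Section 7.1 treats an abnormal laboratory value as an AE only if it causes symptoms, is judged clinically significant or needs therapy. A transient, symptom-free ALP rise might not qualify.

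This does not remove the conflict. The repeat step and the pointer to Table 14-2 concern follow-up of an event already defined by Table 14-1, whereas the reporting sentence in Section 7.3 is tied directly to Table 14-1. No text starts the clock at confirmation. Where the sponsor wants confirmation before action it says so, as in the general principles of Appendix 3 on hyperkalemia; Appendix 2 has no such statement. The general AE test in Section 7.1 does not displace a table that names the value an SAE outright.

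Some of the objection stands. Confirmation first may be clinically reasonable for isolated ALP. Section 7.2.2 refers to submission instructions in the investigator folder, and Section 7.1 refers to alert ranges in Appendix 1; neither is in the text available, and either might clarify practice. Section 8.3 says samples are processed centrally and results sent to the sponsor or its CRO, so for those samples the value itself is not lost, only the SAE report or its timing. The 96-hour figure rests on a borrowed turnaround, and the conclusion does not depend on it.

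**Conclusion.** The concern holds. As written, the isolated-ALP row contradicts Table 14-1 and Sections 7.3 and 7.2.2. For each affected event, the consequence of following the row is either a missing SAE report (value not persisting) or a report 0 to 24 hours late (value persisting, immediate repeat result, filed at once). Longer delays are possible if results take time. These figures assume that the 24-hour clock runs from learning of the first value, which is the only reading the visible text supports. The total number of events cannot be estimated from the documents and may be small. This is a wrong operational safety instruction that should be corrected. It does not affect the sample size, the primary analysis or the SUVr analysis.

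**What to change.** If sites are still active, change the action cell of the isolated-ALP row above 5 x ULN in Table 14-2 to three separate actions: report to the sponsor as an SAE; repeat the liver test within 48 hours; establish causality. The repeat result then goes in as follow-up information, for which Section 7.2.2 already provides.

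If the sponsor prefers confirmation first, that condition must also be written into Table 14-1 and Section 7.3, with a statement of when the 24-hour clock starts.

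If conduct is complete, rewording the row helps little. The latest SAP version is dated 30-Jun-2022, is marked as before database lock, and records that protocol amendment 2.0 was still in effect. In that case, list every ALP value above 5 x ULN, compare the list with the SAEs filed, and resolve any gaps before lock.

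The cost is one table line, or one listing and its reconciliation. Neither adds patient procedures or changes an efficacy or SUVr analysis.
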